1. SAMPLE SIZE AND JUSTIFICATION

A pilot randomized controlled trial with 70 OCS (n=35 for intervention arm; n=35 for control arm) is the most efficient design to accomplish the aims of this pilot study.⁶¹⁻⁶³ For this study, the minimum sample size is calculated using G*Power. Specifying alpha level to be 0.05 (one-sided), expected power to be 0.80, and an expected effect size of 0.50 for the primary outcome (physical function measured by SPPB), the sample size required is 27 per group. Effect size estimates are based on recommendations for clinically meaningful differences for the SPPB^{64,65} and previous pilot randomized controlled trials utilizing the SPBB reporting effect sizes of similar magnitude.^{66,67} Similar designed pilot randomized controlled trials^{38,68-70} used comparable sample sizes to demonstrate acceptability and feasibility.

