Aim 1: Determine the feasibility and acceptability of implementing a 12-week online dietary and resistance training randomized trial with 70 older cancer survivors. This aim will be accomplished by collecting detailed process data, which allows the assessment of accrual, retention, and adherence. Our hypothesis is that we will recruit (within 9 months) 70 OCS, retain $\geq 80\%$ of the sample, and maintain $\geq 80\%$ adherence to the intervention.

Aim 2: Examine the preliminary efficacy of this 12-week online dietary and resistance training intervention with the intervention participants. Registered dietitians and exercise scientists will provide these participants with tailored dietary and resistance training recommendations, counseling, and educational materials. Our hypothesis is that intervention participants will experience statistically significant, clinically meaningful improvements in physical function and associated health outcomes (i.e., muscle strength, dietary quality, HRQoL, self-efficacy,

weight management) after the 12-week dietary and resistance training intervention and at a 3-month post-intervention follow-up.

METHODS

I. STUDY DESIGN

We will examine the feasibility and preliminary efficacy of a 12-week online dietary and resistance training intervention to improve the physical function of OCS through increased protein consumption, healthy eating, and resistance training. In this pilot randomized controlled trial, participants (n=70) will be randomized to one of the two groups: experimental (online counseling, menus, educational materials) and enhanced control (passive educational materials). We will examine the intervention effects on physical function and associated health outcomes during the 12-week period between the experimental and control group.

II. PARTICIPANT SELECTION

1. *ELIGIBILITY CRITERIA*

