Aim 2: The primary outcome of the SPPB will be assessed at three time points: baseline, end-of-study, and 3-month follow-up. Efficacy will be based on 12 weeks. The SPPB score is a continuous variable, collected as the total score ranging from 0-12. Group differences in SPPB scores over the time will be tested using repeated measures ANOVA (SAS PROC MIXED). Using the planned contrasts command, we will investigate the changes in SPPB scores within each group, and between the intervention and control groups at end-of-study. Descriptive statistics and frequency distributions will be used to characterize the sample. To examine the effect of the intervention on the changes in physical function, a linear mixed effect model will be adopted using SAS PROC MIXED procedure. The intervention group (intervention vs. control) and time points (baseline, end-of-study, 3-month follow-up) serve as the categorical predictors, together with the intervention*time interaction term. A significant intervention*time interaction effect would indicate a differential change pattern over the time between the groups. Using post-hoc contrasts, we will compare group differences in all collected variables at each time point. Using planned contrasts command, we will investigate for each group the change from baseline to end-of-study, from end-of-study to 3-month follow-up, and from baseline to 3-month follow-up to capture the change patterns over the phases and Bonferroni correction will be applied. Preliminary effect sizes will be generated to inform future trials. A Shapiro-Wilk test, skewness, kurtosis, and Q-Q plots will be used to assess normality of survivor baseline and end-of-study outcomes. Based on normality tests, change in participant outcome measures from baseline to end-of-study will be assessed using paired t-tests or Wilcoxon's signed rank tests.⁷⁶ Analysis will be carried out using intent-to-treat (all participants) and modified intent-to-treat (adherent participants only). All quantitative analyses will be performed using SAS version 9.4.

REFERENCES References

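### The 27 per group for 80% power fits a within-arm paired test; with 0.50 in SDs of the analysed quantity, the between-arm SPPB contrast needs 51 per arm and has 66.5% power at 35 per arm

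*Combined protocol and SAP*

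**What the plan says.** Section V.1 (Sample Size and Justification) gives these inputs for the SPPB, the primary outcome: "Specifying alpha level to be 0.05 (one-sided), expected power to be 0.80, and an expected effect size of 0.50". It concludes that "the sample size required is 27 per group" and plans 35 per arm. It cites G*Power but names no test, and it gives no SD, correlation or allowance for dropout.

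Other sections describe two kinds of comparison.

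- **Between arms.** Section I (Study Design): "We will examine the intervention effects on physical function and associated health outcomes during the 12-week period between the experimental and control group". Section V.2 (Data Analysis Plan), Aim 2, fits a model with an intervention-by-time term and adds planned contrasts: "we will investigate the changes in SPPB scores within each group, and between the intervention and control groups at end-of-study". The time point for efficacy is fixed there: "Efficacy will be based on 12 weeks".
- **Within arm.** The Aim 2 hypothesis in the Specific Aims concerns the intervention arm: "Our hypothesis is that intervention participants will experience statistically significant, clinically meaningful improvements in physical function". Section V.2 adds that "change in participant outcome measures from baseline to end-of-study will be assessed using paired t-tests" or a signed rank test. It also plans within-group contrasts between time points, "to capture the change patterns over the phases and Bonferroni correction will be applied".

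Section V.2, Aim 1, sets the retention goal at 80%, which is 56 of 70.

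**The concern.** A reader who sees a number per group in a two-arm randomised trial will take the 80% as power for the difference between the arms. For a two-sample test with an effect of 0.50, 27 per arm is far too few. It is about what a paired test within one arm needs.

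This is the only power statement for the primary outcome and the only calculation behind 35 per arm. A change within the intervention arm cannot be separated from the effects of time, practice or regression to the mean; the 35 controls are there to make that separation. If the stated power belongs to the paired test, the randomised comparison has no stated power. A null between-arm result could then be read as if the trial had had an 80% chance of finding the effect.

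**Working it through.** **Inputs.** From V.1: effect size 0.50, one-sided alpha 0.05, power 0.80, 35 per arm. From V.2, Aim 1: 80% retention, so 56 of 70, or 28 per arm if loss is equal (an assumption). All powers use the exact non-central t distribution.

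**Step 1: reproduce the plan's 27.** For a paired or one-sample t-test, df = n − 1 and the non-centrality is 0.50 × √n.

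- n = 26: non-centrality 2.550, critical t 1.708, power 79.8%.
- n = 27: non-centrality 2.598, critical t 1.706, power 81.2%.

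So 27 is the smallest n that reaches 80%. Inflating for 20% loss gives 27/0.80 = 33.75, or 34, close to the planned 35. V.1 does not name the paired test; it is inferred from this match.

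The match holds only at unadjusted alpha. If the Bonferroni correction covers three contrasts per arm (an assumption about the family), alpha is 0.05/3 and paired power at n = 27 is 63.9%.

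**Step 2: the same inputs for the between-arm contrast.** For a two-sample t-test, df = 2n − 2 and the non-centrality is 0.50 × √(n/2). Here 0.50 is in SDs of the quantity analysed, such as change from baseline to 12 weeks.

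| n per arm | Non-centrality | Power, one-sided | Power, two-sided |
|---|---|---|---|
| 27 | 1.837 | 56.7% | 43.8% |
| 28 | 1.871 | 58.0% | 45.1% |
| 35 | 2.092 | 66.5% | 54.1% |
| 50 | 2.500 | 79.9% | 69.7% |
| 51 | 2.525 | 80.6% | 70.6% |
| 64 | 2.828 | 87.9% | 80.1% |

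The requirement is 51 per arm one-sided. Two-sided it is 64, since 63 per arm gives 79.5%. The effect detectable with 80% power is 0.60 SD at 35 per arm and 0.67 SD at 28 per arm one-sided, or 0.68 and 0.76 two-sided.

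**Step 3: what if 0.50 is in raw SPPB SDs?** With a baseline to 12-week correlation ρ, the effect on the analysed scale becomes 0.50/√(2(1 − ρ)) for a change score, or 0.50/√(1 − ρ²) with baseline adjustment. V.1 gives no ρ, so the values below are assumptions. Power is one-sided.

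| ρ | Change score, 28 / 35 per arm | Baseline-adjusted, 28 / 35 per arm |
|---|---|---|
| 0.5 | 58.0% / 66.5% | 68.7% / 77.2% |
| 0.6 | 66.3% / 74.9% | 74.7% / 82.7% |
| 0.7 | 77.0% / 84.8% | 82.7% / 89.5% |
| 0.8 | 89.9% / 94.8% | 92.4% / 96.5% |

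For 27 per arm to reach 80%, ρ must be about 0.73 (change score) or 0.68 (baseline-adjusted). At 35 per arm the thresholds are about 0.65 and 0.55.

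**Step 4: other routes to 27.** A repeated-measures interaction F-test with two groups and three time points gives 54 in total, or 27 per group, if f = 0.25 and the correlation is zero. With the stated 0.50 used as f, the same test needs only 16 in total. This route therefore requires an effect size other than the one stated, an unstated correlation, and an F-test, which is not one-sided.

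**The case against.** The strongest reply is that 27 is correct for a test that the plan contains. The Aim 2 hypothesis is about improvement in intervention participants, paired tests are planned, and the sentence on efficacy fixes a time point without naming a comparison. V.1 never says that its 80% is for the between-arm contrast. All of this is true. What it shows is that the stated power belongs to the within-arm test and that the randomised comparison has none.

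The second reply is that 51, 66.5% and 58.0% depend on the scale of 0.50. This stands as a condition. V.1 links the value to clinically meaningful SPPB differences, so raw SDs are possible, and with a high enough correlation 35 per arm would be adequate. But V.1 states neither the scale nor a correlation, so this cannot be claimed as support for 27.

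The third reply is that this is a pilot, with feasibility as Aim 1, and that V.1 also justifies its size by comparable pilot trials. A pilot need not be powered for efficacy, and this is a good reason to leave n alone. It does not excuse a power figure that fits a different comparison, particularly when Aim 2 predicts statistical significance and the effect sizes are to inform later trials.

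**Conclusion.** The concern holds. On the stated inputs, 27 per group gives 80% power only for a within-arm paired test at unadjusted alpha. For the between-arm contrast at 12 weeks, with 0.50 in SDs of the analysed quantity, the chance of missing the effect one-sided is 33.5% at 35 per arm and 42.0% at 28 per arm. Two-sided it is 45.9% and 54.9%. The 20% implied by the stated power does not apply to that contrast.

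The arithmetic is exact; two points rest on assumption. The paired test is inferred because it reproduces 27, and the 28 per arm supposes equal loss at exactly 80% retention. Reading 0.50 in raw SDs could raise between-arm power above 80%, but only with a correlation that the plan would have to state and support. V.2 also does not say whether the 12-week contrast keeps the one-sided rule used in V.1; as a single-degree-of-freedom contrast, it can be tested one-sided.

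**What to change.** Keep n = 70. Confirm from the G*Power record which test was run. If it was the paired test, rewrite the calculation in V.1 along these lines:

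> Twenty-seven per arm gives 81% power for a within-arm change of 0.50 SD of change (paired t-test, one-sided alpha 0.05, unadjusted). For the between-arm difference in 12-week SPPB change, an effect of 0.50 SD of change has 66.5% power at 35 per arm and 58.0% at 28 per arm, one-sided (54.1% and 45.1% two-sided). The effects detectable with 80% power are 0.60 and 0.67 SD one-sided (0.68 and 0.76 two-sided).

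If another test was run, name it with all its inputs and still give the between-arm power. If 0.50 is meant in raw SPPB SDs, say so, state the assumed baseline to 12-week correlation with its source, and give the power that follows. In V.2, state the sidedness of the 12-week between-arm contrast so that it agrees with V.1.

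The cost is one paragraph in V.1 and one phrase in V.2, with no extra participants. The stated between-arm power becomes less favourable.

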2. DATA ANALYSIS PLAN

Aim 1: The feasibility of implementing a 12-week online diet and resistance training intervention with OCS will be determined by the study accrual rate, retention rate, and adherence rate. The study accrual rate will be calculated by dividing the number of potential participants that passed screening by the total number of participants started in the study after appropriate informed consent procedures. The recruitment goal is set at 70 participants recruited over a 9-month period. Retention rate will be calculated by dividing the total number of participants initiated by total number of participants in the study at baseline and 12 weeks (end-of-study). Retention goal for this trial is 80%. If 80% (56/70) of participants are retained at end-of-study, the retention goal for this trial will be achieved. Previous studies by the study team had similar recruitment and retention rates of older participants.⁷¹⁻⁷³ We are confident in our ability to recruit and retain the study participants necessary to conduct the proposed study. Participants will be determined to be adherent if they attend ≥80% of the intervention sessions (in-person meetings with study staff and online intervention sessions).^{71,74,75} Overall adherence and

retention rates and associated 95% confidence intervals will be reported at baseline, end-of-study, and 3-month follow-up.

Aim 2: The primary outcome of the SPPB will be assessed at three time points: baseline, end-of-study, and 3-month follow-up. Efficacy will be based on 12 weeks. The SPPB score is a continuous variable, collected as the total score ranging from 0-12. Group differences in SPPB scores over the time will be tested using repeated measures ANOVA (SAS PROC MIXED). Using the planned contrasts command, we will investigate the changes in SPPB scores within each group, and between the intervention and control groups at end-of-study. Descriptive statistics and frequency distributions will be used to characterize the sample. To examine the effect of the intervention on the changes in physical function, a linear mixed effect model will be adopted using SAS PROC MIXED procedure. The intervention group (intervention vs. control) and time points (baseline, end-of-study, 3-month follow-up) serve as the categorical predictors, together with the intervention*time interaction term. A significant intervention*time interaction effect would indicate a differential change pattern over the time between the groups. Using post-hoc contrasts, we will compare group differences in all collected variables at each time point. Using planned contrasts command, we will investigate for each group the change from baseline to end-of-study, from end-of-study to 3-month follow-up, and from baseline to 3-month follow-up to capture the change patterns over the phases and Bonferroni correction will be applied. Preliminary effect sizes will be generated to inform future trials. A Shapiro-Wilk test, skewness, kurtosis, and Q-Q plots will be used to assess normality of survivor baseline and end-of-study outcomes. Based on normality tests, change in participant outcome measures from baseline to end-of-study will be assessed using paired t-tests or Wilcoxon's signed rank tests.⁷⁶ Analysis will be carried out using intent-to-treat (all participants) and modified intent-to-treat (adherent participants only). All quantitative analyses will be performed using SAS version 9.4.

REFERENCES References

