Eligibility criteria are: ≥ 65 years of age, a primary diagnosis of stage I-III breast, colorectal, and prostate cancer, completion of primary curative treatment, reported at least 1 physical function limitation on the PFSS ("limited a little", "limited a lot"), no evidence of progressive disease or second cancers, community-dwelling, and able to provide consent. The 3 cancer types are chosen because they are the most common cancer types³⁵ with high 5-year survival rates.³⁶ Additionally, most of the evidence of the benefits of exercise and diet has occurred in survivors diagnosed with breast, prostate, or colorectal cancer.^{24,37-39} Individuals are excluded if they currently receive cancer treatment (e.g., chemotherapy, radiation), have liver and/or renal disease limiting their protein intake, are under the care of a RD/nutritionist, participating in other diet/exercise interventions, consume protein supplements, and have contraindications to unsupervised exercise (e.g., walker/wheelchair use).

2. *RECRUITMENT*

Five methods will be employed to recruit potential participants:

1. Flyers distributed at the JamesCare for Life programs (wellness programs offered through the Ohio State University Comprehensive Cancer Center (OSUCCC)) as well as through their email list of cancer survivors. Flyers will also be distributed at the OSUCCC's Cancer and Aging Resiliency (CARE) clinics, multidisciplinary clinics designed to address the unique needs of older cancer survivors, and the OSUCCC GI Medical Oncology Clinic. The study will be advertised on the flyer and eligible women and men will be requested to contact the research assistant if they are interested in study participation.

2. In-person during follow-up visits at the Survivorship Clinic and CARE clinics within OSUCCC by study team member ([name]). When prospective patients are identified, the provider will provide the prospective participant with the recruitment flyer that has the PI and research assistant's names and contact information. In addition, the research assistant will be in the clinics screening eligible participants by appointment date and meeting the potential participants in person to recruit them.

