Research Match will also be used to recruit potential participants. ResearchMatch is a free and secure online tool created by academic institutions across the country to share study and PI contact information to potentially eligible participants. Potentially eligible participants will receive an email introduction to the study and, if they are interested, permit ResearchMatch to release their contact information to the study team. The research assistant will then contact potential participants, via email or phone, to explain study requirements, and confirm eligibility (≥65 years of age, history of stage 1-3 breast, colorectal, and prostate cancer, completed primary cancer treatment, and have an email address).

5. OSUCCC-James Cancer Program Analytics services will be used to generate a list of OSUCCC patients meeting the study criteria.

Email: Potential participants with email addresses will be emailed an invitation letter, signed by OSUCCC providers, to participate in the study. An informational overview of the study and time commitment will also be provided in the invitation. Potential participants interested in the study will be instructed to contact the Clinical Research Coordinator to discuss any questions and complete the screening questionnaire to confirm eligibility.

B. Recruitment Locations

Recruitment will occur at the Survivorship Clinic and CARE clinics within OSUCCC. Recruitment will occur in the clinic exam rooms and/or the waiting room at these clinics. As noted in the facilities page, OSUCCC is the third largest cancer hospital in the nation. The hospital includes a 36-bed blood and marrow transplant unit, inpatient units in which sub-specialists focus on just one type of cancer, a cancer clinical trials unit, 14 state-of-the-art operating rooms, six interventional radiology suites, special isolation rooms, chemotherapy and transfusion areas, and seven linear accelerators for radiation therapy. The Survivorship Clinic at OSUCCC is one of the country's largest cancer supportive care programs, with about 40 team members. The Cancer and Aging Resiliency (CARE) clinics at OSUCCC provides each older adult with cancer with a comprehensive, multidisciplinary treatment plan. Study team member, [name], is the director of the CARE clinics located at the OSUCCC.

C. Recruitment Follow-up

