The research assistant will send out a reminder mailing to all identified participants two weeks after the initial study contact. The research assistant will make at three attempts by phone to reach the non-responders. If no response is given after the third attempt, the potential participant will be considered a "non-responder."

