4. DATA TO BE COLLECTED

We are collecting data using all validated measures. Our main outcome is physical function which will be measured by The physical performance assessment, Short Physical Performance Battery (SPPB)⁵⁴, will measure physical function at baseline, end-of-study, and follow-up. The SPPB includes three lower extremity physical performance measures (standing balance, five consecutive chair rises, 4-meter gait walk at usual pace) to assess lower extremity strength.

Secondary outcomes will be:

- *Acceptability.* At end-of-study, intervention group participants will complete a 5-item, Likert-scale questionnaire, with written comments, regarding their preferences for receiving education and counseling, successes and challenges, program satisfaction, and suggestions for improvement.
- *Feasibility.* Intervention feasibility will be measured by rates of accrual, retention, and adherence at baseline, end-of-study, and 3-month follow-up. Recruitment rate is based on Consolidated Standards of Reporting Trials criteria⁵⁵ that includes eligible consented individuals and eligible non-consented individuals with non-recruitment reasons documented. Process information (number/duration of video visits) will be recorded.
- *Muscle Strength.* Handgrip strength will be measured at baseline, end-of-study, and follow-up in both hands using a hydraulic grip strength dynamometer (Jamar Model 7498).
- *Dietary Quality.* Protein intake and dietary quality will be assessed at baseline and end-of-study by the National Cancer Institute's DHQIII.⁵⁶
- *Resistance exercise.* Self-reported resistance exercise will be assessed using the revised version of The Godin-Shephard Leisure-Time Exercise Questionnaire (LTEQ) modified to specifically capture self-reported resistance exercise participation.
- *HRQoL.* RAND-36 Health Status Measure⁵⁷ is comprised of 8 subscales assessing multiple aspects of HRQoL. Physical and mental component summaries are created. All scores range from 0-100, with 100 as the highest.
- *Self-efficacy.* Baseline and end-of-study self-efficacy for diet and resistance training will be measured by: "How sure are you that you could do exercises to make your body stronger for 15 minutes, 3 days a week?" and "How sure are you that you could improve your diet?"

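### The Aim 1 accrual rate is written upside down and, even when corrected, covers only people already screened as eligible, so it says nothing about uptake among those approached

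*Combined protocol and SAP*

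**What the plan says.** Section V.2, Data Analysis Plan, makes accrual one of three rates that determine feasibility under Aim 1, with retention and adherence. The accrual rate is found by "dividing the number of potential participants that passed screening by the total number of participants started in the study", after informed consent. The target beside it is a count: 70 participants in 9 months.

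Section 4, Data to be Collected (Feasibility), describes a recruitment rate based on CONSORT criteria, one that "includes eligible consented individuals and eligible non-consented individuals with non-recruitment reasons documented". Section V.2 does not refer to it.

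Two of the five recruitment methods in section II.2 begin from records. Under method 5 an analytics service "will be used to generate a list of OSUCCC patients meeting the study criteria"; those with an email address are invited and, if interested, are to contact the coordinator and "complete the screening questionnaire to confirm eligibility". Under method 3 the registry's own staff telephone people selected on the eligibility criteria and ask whether the study may contact them. Recruitment Follow-up provides a reminder mailing and three telephone attempts: "If no response is given after the third attempt, the potential participant will be considered" a non-responder. Nothing says how non-responders enter any rate.

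**The concern.** There are two problems. First, the numerator and denominator are exchanged, so the ratio as written is not a proportion of anyone who could have joined.

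Second, the corrected ratio starts late in the recruitment path. Losses from unanswered emails and calls, or from refusing the registry's request, happen before screening and leave no trace in it. The Timeline section itself lists participation rates among the factors limiting enrolment, yet the planned rate does not capture participation before screening. A team using this pilot to plan a larger trial would know how many screened-in people enrol, but not how many records must be worked through to find them.

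**Working it through.** **Direction of the ratio.** Let S be the number started and P the number who passed screening. Everyone in S is also in P, so P ≥ S and the written ratio P/S is at least 1. With S = 70 (the plan's target) and P = 100 (assumed):

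- as written: 100/70 = 143%
- turned over: 70/100 = 70%

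The retention sentence in the same section has the same inversion, and there the plan supplies its own check. Its words divide participants initiated by participants remaining, which gives 70/56 = 125%. Its worked example is 56/70 = 80%. That example supports reading the accrual rate as S/P.

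**Who is counted.** The S/P ratio involves only people who reached and passed screening. A non-responder, or a registry patient who refuses contact, is in neither S nor P.

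**What is known about those left out.** Records alone do not settle eligibility. Section II.1 requires that the person has "reported at least 1 physical function limitation on the PFSS". On the registry route, study staff administer that questionnaire after permission and contact; on the analytics route, a screening questionnaire still has to be completed. A silent listed patient is therefore of unknown eligibility.

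**How the rate would move.** The documents give neither the number of non-responders (NR) nor the share of them who are eligible (e). Uptake among all eligible people, responding or not, would be S/(P + e × NR). With S = 70 and P = 100:

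| NR (assumed) | e = 0 | e = 0.25 | e = 0.5 | e = 1 |
|---|---|---|---|---|
| 100 | 70% | 56% | 46.7% | 35% |
| 400 | 70% | 35% | 23.3% | 14% |

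The difference from 70% runs from nothing to a factor of five (70/14), depending entirely on two unknowns.

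**Yield per person contacted.** This figure does not need e. If, for simplicity, everyone came through the list-based routes, the denominator would hold at least P + NR people, plus screen failures and those who declined contact. The yield is then at most 70/200 = 35% with 100 non-responders and at most 70/500 = 14% with 400. In planning terms, that is at least 200/70 = 2.9 or 500/70 = 7.1 contacts per participant, against 100/70 = 1.4 screened-in people.

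**The two definitions side by side.** People who passed screening can be exactly the eligible consented plus the eligible non-consented, so S/P and the CONSORT-based rate can coincide. They differ if someone consents but is not randomised, and the plan does not say which event counts as starting. Neither definition mentions non-responders.

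**The case against.** The strongest reply is that enrolment among screened-eligible people is a legitimate and common feasibility measure, that the inversion is an evident slip, and that the Aim 1 accrual goal is a count which no choice of denominator can affect. All of that stands. It means the rate should be kept, right way up, and that no success criterion is at risk.

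A reader might go further and infer any of three things that the documents do not support.

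- *That known eligible patients are dropped.* A list said to meet the study criteria invites this, but the self-reported function limitation and exclusions such as protein supplement use or participation in another diet or exercise programme are confirmed only at screening.
- *That section V.2 contradicts the CONSORT-based definition.* That definition is also limited to eligible people. The two texts are worded differently and need one denominator, but they do not disagree about non-responders.
- *That the plan overstates uptake by a definite amount.* The written ratio is not an uptake figure at all. The corrected one is a valid rate for a narrower group, which could be misread as uptake among those approached; by how much cannot be said.

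The burden is also more than a recount of the study team's own calls. On the registry route the first calls are made by registry staff, and one patient may be reachable by several routes, so careless tallies would count people twice.

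**Conclusion.** The point holds in a limited form. The accrual ratio is inverted, as the parallel retention example shows, and its corrected form describes enrolment only after response and screening. It therefore cannot inform Aim 1 about uptake among those approached through the analytics list or the registry. The two descriptions of the rate should be reconciled.

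Its size is not determinable from the documents. The range of 70% down to 14% rests on assumed counts and shows only that the gap could be nil or large. The effect is on a descriptive feasibility rate and its use in planning. The count of 70 in 9 months and the efficacy analysis are unaffected. This is a low-cost improvement to reporting.

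**What to change.** 1. In section V.2, define the accrual rate as participants randomised divided by people who passed screening. Align section 4 with it as eligible consented over eligible consented plus eligible non-consented, and state how a person who consents but is not randomised is counted. Turn the retention ratio the same way, to match 56/70.
2. For the analytics-list and registry routes, add a separately labelled recruitment yield: randomised divided by all record-identified patients contacted. Report the numbers contacted, non-responding (eligibility unknown), declining contact, screened, eligible, consented and randomised, with each person assigned to one route.

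The cost is revised wording, a contact log that includes the calls made by registry staff, a rule for assigning route, and a second figure that will look less favourable than the first. No change to sample size, visits or the recruitment goal is needed.

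### The retention and accrual formulas are upside down: retention as written gives 125% where the same paragraph works it as 80% (56/70)

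*Combined protocol and SAP*

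**What the plan says.** Under Aim 1, section V.2 (Data Analysis Plan) makes feasibility depend on three rates: accrual, retention and adherence. Two of them are given as formulas.

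- Accrual is obtained by "dividing the number of potential participants that passed screening by the total number of participants started in the study", counting those who start after informed consent.
- Retention is obtained by "dividing the total number of participants initiated by total number of participants in the study at baseline and 12 weeks", the latter being end-of-study.

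The same paragraph then gives the retention target with a worked figure: "If 80% (56/70) of participants are retained at end-of-study, the retention goal for this trial will be achieved". It sets the accrual target as a number of people: "The recruitment goal is set at 70 participants recruited over a 9-month period". For adherence and retention it promises that "retention rates and associated 95% confidence intervals will be reported at baseline, end-of-study, and 3-month follow-up".

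Two other places bear on the intended direction. Aim 1 in the Specific Aims states the retention hypothesis as at least 80% of the sample, and the recruitment hypothesis as a count: "Our hypothesis is that we will recruit (within 9 months) 70 OCS". The Feasibility item in section 4 (Data to be Collected) describes a recruitment rate that "includes eligible consented individuals and eligible non-consented individuals with non-recruitment reasons documented".

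**The concern.** A retention rate is the share of those who began who are still in the study, so the starting number belongs in the denominator. The plan puts it in the numerator. An accrual rate is ordinarily the share of eligible people who enrol; the plan puts the eligible on top and the enrolled underneath.

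Both written ratios are therefore bounded below by 100% and move the wrong way: the worse the retention or uptake, the higher the reported rate. Against an 80% target, the retention ratio as written can never fail. The planned confidence intervals are affected too, because a quantity that is at least 1 is not a binomial proportion and the usual interval for a proportion does not apply to it. Since this is a pilot whose first aim is feasibility, these rates are among its main results.

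**Working it through.** **Inputs**

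- Participants initiated: 70, 35 per arm (section V.1, Sample Size and Justification).
- Participants retained at 12 weeks in the plan's own example: 56 (section V.2, Aim 1).
- Retention goal: 80% (section V.2, Aim 1; also Aim 1 of the Specific Aims).
- Number passing screening: not given, so treated below as an assumption over a range.

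**1. Reproducing the plan's retention figure**

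- As written, at 12 weeks: initiated / in study = 70/56 = 1.25, or 125%. This is not 80%.
- As written, at baseline: 70/70 = 1.00, or 100%. This is not 80% either, and it is the same in both directions, so baseline cannot discriminate.
- Terms swapped, at 12 weeks: in study / initiated = 56/70 = 0.80, or 80%. This matches exactly.

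The worked figure is right and the formula is wrong.

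**2. How the written retention ratio behaves**

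| Retained of 70 | As written (70/retained) | Swapped (retained/70) | Goal of 80% met? |
|---|---|---|---|
| 63 | 111% | 90.0% | yes |
| 56 | 125% | 80.0% | yes |
| 55 | 127% | 78.6% | no |
| 49 | 143% | 70.0% | no |
| 35 | 200% | 50.0% | no |

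The last column judges the swapped rate. The written ratio exceeds 80% in every row and increases down the table as retention falls.

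**3. Accrual**

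Everyone who starts must first have passed screening, so passed / started cannot be below 1. With 70 starting and an assumed number passing screening:

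| Passed screening (assumed) | As written (passed/70) | Swapped (70/passed) |
|---|---|---|
| 70 | 100% | 100% |
| 100 | 143% | 70% |
| 140 | 200% | 50% |
| 200 | 286% | 35% |

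The direction does not depend on the assumed counts; only the size does. Section 4 names eligible people who consented and eligible people who did not. Together these make up all eligible people, the natural denominator of a proportion enrolled.

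**4. Interval for the corrected retention rate**

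Wilson 95% interval with p = 0.80, n = 70, z = 1.96, z² = 3.8416:

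- Centre: (p + z²/2n) / (1 + z²/n) = (0.80 + 0.0274) / 1.0549 = 0.784.
- Half-width: z × √(p(1−p)/n + z²/4n²) / (1 + z²/n) = 1.96 × √(0.002286 + 0.000196) / 1.0549 = 0.0926.
- Limits: 69.2% to 87.7%. The exact (Clopper-Pearson) limits are 68.7% to 88.6%.

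**The case against.** The strongest reply is that this is a slip of wording which the paragraph corrects for itself. The retention criterion is given in counts with its direction shown, the Specific Aims repeat it as a share of the sample, and an analyst who obtained a retention rate above 100% would be expected to notice. On that reading no decision changes. This stands as a limit on the consequences: the intended retention criterion is not in doubt. It does not remove the contradiction, because the formula is the stated calculation rule and it disagrees with the figure it is meant to produce.

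The second reply concerns accrual. It has no worked example and no percentage target, and passed-screening over started is a coherent quantity in itself: eligible people per enrolment. Section 4 speaks of a recruitment rate, not an accrual rate, and names components without saying which goes on top. So the evidence on accrual is indirect, and weaker than for retention. Three things still favour reversal: the plan calls the quantity a rate and uses it to judge feasibility, a ratio that rises as uptake falls cannot serve that purpose, and the neighbouring retention formula has the same inversion. The lack of a worked figure also means that a reversed accrual rate is less likely to be caught.

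**Conclusion.** The concern holds. For retention the plan contradicts its own figure: 125% by the formula against 80% by the worked example at 12 weeks. This rests on no assumption beyond the plan's 56 and 70. For accrual the reversal is an inference from the name and purpose of the rate and from the components listed in section 4; the size of the distortion depends on the number passing screening, which is unknown in advance (143% against 70% if 100 pass, 200% against 50% if 140 pass).

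Two of the three reported feasibility rates should be corrected before analysis. The recruitment goal, being a count of 70 in 9 months, is unaffected, as are the sample size and the Aim 2 analysis.

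**What to change.** Rewrite two sentences in section V.2, Aim 1:

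- **Accrual rate** = participants who consented and started, divided by all who passed screening (eligible consented plus eligible non-consented). Use the same terms in the Feasibility item of section 4, so that accrual rate and recruitment rate are visibly one measure or, if two are meant, are defined separately.
- **Retention rate** = participants still in the study at the time point, divided by participants initiated. Name both 12 weeks and the 3-month follow-up, since the plan reports retention at both but the formula mentions only baseline and 12 weeks.

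State that the planned 95% intervals for retention are binomial intervals on the corrected proportion; Wilson or exact would serve.

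The change costs a few lines of text. It needs no new data, since section 4 already commits the trial to recording eligible people who do not consent, and no change in procedures.
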